4. RADIOISOTOPES OR RADIATION MACHINES

a. Standard of Care (SOC) Procedures

Identify Week/Month of Study	Name of Exam	Identify if SOC or Research
N/A	N/A	N/A

b. Radioisotopes

None

c. Radiation Machines – Diagnostic Procedures

None

d. Radiation Machines – Therapeutic Procedures

- i. Area treated, dose per fraction/number of fractions, performed as part of normal clinical management or due to research participation (well-established procedures)

N/A

- ii. FDA status of the machine, basis for dosimetry, area treated, dose per fraction and number of fractions (if procedure is not well-established)

N/A

5. DEVICES USED IN THE STUDY

a. Investigational Devices (Including Commercial Devices Used Off-Label)

None

b. IDE-Exempt Devices

None

6. DRUGS, BIOLOGICS, REAGENTS, OR CHEMICALS USED IN THE STUDY

a. Investigational Drugs, Biologics, Reagents, or Chemicals

None

b. Commercial Drugs, Biologics, Reagents, or Chemicals

None

7. DISINFECTION PROCEDURES FOR MEDICAL EQUIPMENT USED ON BOTH HUMANS AND ANIMALS

N/A

8. PARTICIPANT POPULATION

- a. Planned Enrollment
 - (i) We expect to enroll 60 participants at Stanford.
 - (ii) We expect to enroll 60 participants total at all sites. Stanford is the only site of this study.
 - (iii) Healthy, adult females 18-40 are the target population for this eating disorder prevention program. Using participants that fit this description enables the research team to evaluate the effectiveness of virtual delivery versus in-person delivery of this prevention program and discern the specific factors that may contribute to virtual delivery being more effective in reducing eating disorder risk factors and symptoms and risk for future eating disorders.

- b. Age, Gender, and Ethnic Background

Target participants will be females age 18-40, we will not exclude on the basis of ethnic background.

- c. Vulnerable Populations

Young adult females are included in this study because they are at elevated risk for future eating disorder onset. Information on the risks and benefits of the program and their rights and welfare will be addressed in the Informed Consent forms.

If participants are too young (below 18), they will be excluded from this study. We plan to ask for dates of birth from all interested participants during the screener in order to determine if they are at an appropriate age to participate in the study. Dates of birth from all interested participants will be required during the screener in order to determine if they are at an appropriate age to participate in the study.

- d. Rationale for Exclusion of Certain Populations

The purpose of this study is to evaluate two delivery methods for a body acceptance/eating disorder prevention class to test whether the program is more effective when implemented virtually. Children are not the target population of this study, as we are examining the effectiveness of the program in adult women, which are typically above 18 years of age.

- e. Stanford Populations

Stanford students, employees, or laboratory personnel may be eligible to participate in the research study. We cannot estimate how many that might be. If any such participants are enrolled, they will follow standard procedure as any participant would and complete a consent form.

- f. Healthy Volunteers

The target population of this study are healthy participants due to its preventative nature as a body acceptance class. The risks for healthy volunteers is extremely low. There is potential for participants to feel distressed when disclosing personal information during

the assessment visits or during the group sessions. However, based on previous experience, the associated risk of this occurring is a very low and the effects would be short-lived. These assessments have been used by thousands of young women with almost no distressing outcomes.

There is a small risk that healthy volunteers may experience some psychological stress as a result of finding out new information about their psychological health that was revealed in the course of the study. However participants are fully informed of these risks at the time of consent. All collected information is kept confidential in order to protect participant's identity and participants are informed that they are free to exercise their right to withdraw from the study at any time without adverse consequence.

g. Recruitment Details

Recruitment will take place using both online and in person strategies.

In person - flyers will be posted in high traffic community areas on Stanford's campus (dorms, dining halls, learning hubs, student health services, etc.)

Online - Ads will be posted on the internet using social media sites: Facebook and Instagram, community forums: Craigslist and Reddit, and e-mails sent to community listservs. We will manage an instagram and facebook page with postings about the study using the approved images and captions. All posts on the page will be moderated and set to block commenting or posting by the public. Posting of online ads will be managed based on inclusion criteria, i.e. Stanford students, age, etc.

Social media recruitment posts will be set up such that the security settings do not allow participants or others from the public to post on the wall/public forum. If this is not possible due to the social media platform's settings, the social media posts will be monitored and any disclosures of PHI removed.

Once the potentially eligible participants complete the screener we will reach out to them via email or telephone to clarify points of eligibility, and if eligible, schedule an assessment.

Additionally, all families who call the Stanford clinic for services are asked about their willingness to be contacted for research. Individuals who may potentially meet study inclusion criteria will be called and asked if they are willing to hear about a Stanford research study.

h. Eligibility Criteria

i. Inclusion Criteria

- i. Female
- ii. Ages 18 - 40

iii. Fluently speak and read English and have access to a computer or tablet with internet
iv. Must live within the United States

ii. Exclusion Criteria

N/A

i. Screening Procedures

Interested participants will be asked to fill out a brief online screening questionnaire. Only information pertaining to the inclusionary & exclusionary criteria will be included in the questionnaire. Participants have the option to terminate the online screening questionnaire at any time. The participant will be contacted to schedule an assessment upon review of their questionnaire. For participants that complete the online screener, the participants rights will be clearly stated before proceeding with the screening. Additionally, they can call the research personnel prior to continuing if they have any questions.

j. Participation in Multiple Protocols

As a part of the informed consent process, subjects will be asked if they are participating in any other research projects. Their participation in other protocols will not exclude them from participation in this study.

k. Payments to Participants

N/A

l. Costs to Participants

N/A

m. Planned Duration of the Study

The estimated duration of the entire study is eight months, in line with the timeline for completion of a Master's thesis and summer quarter conferral.

- i. The screening will consist of the online questionnaire (about 10 minutes), and the baseline assessment (about 1-2 hours).
- ii. Active participation will be 4 months (4 weeks of Body Project sessions, and 3 month follow-up assessment)
- iii. Analysis of participant data will take about 2-3 months.

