This pilot study is comparing the effects of a virtual delivery versus in-person delivery of an eating disorder prevention program. Everyone in the trial will receive the Body Project, an effective eating disorder prevention program, meaning that everyone who participates will benefit. There will be no alternative courses of treatment to offer. This program is designed for prevention, to prevent the likelihood of onset of an eating disorder. Thus, it is not intended to treat any conditions. The only other alternative would be to not participant in this study. There are no known risks associated with participation in this eating disorder prevention program, although some sensitive topics may cause participant's discomfort. This program has the potential to aid participants in resolving some or all struggles and difficulties with body image. Additionally, this study will not hinder participants with a DSM-5 eating disorder from continuing or pursuing any outside treatment whilst they are enrolled in the study. Previous research has shown that there are stronger reductions in eating disorder symptoms for participants with a DSM-5 eating disorder than participants without an eating disorder.

f. Will it be possible to continue the more (most) appropriate therapy for the participant(s) after the conclusion of the study?

If there are participants who meet criteria for a DSM-5 eating disorder at the termination of the study, the appropriate referrals will be provided. This study will not interfere with their current levels of care or their future levels of care.

g. Study Endpoint(s)

If there is such a discrepancy between the two different conditions, they will be evaluated by the principal investigators in terms of terminating the study prematurely. Otherwise, we shall examine the program's effectiveness at the end of the study and study participation will be completed within 24-weeks, including a 3-month follow up after the conclusion of Body Project groups.

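### Women with a current eating disorder can enter a study whose participants are called healthy, and the only diagnosis-tied referral in the available protocol text is at study termination, although the EDDI is given from baseline

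*Protocol*

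**What the plan says.** **Population.** Protocol 8a(iii) says "Healthy, adult females 18-40 are the target population for this eating disorder prevention program", and its next sentence applies that description to the participants used in the study. Section 8f repeats the label and adds "The risks for healthy volunteers is extremely low". The eligibility list in 8h asks for female sex, age 18 to 40, fluent English with a computer or tablet and internet, and US residence. Its exclusion entry is N/A. On screening, 8i says "Only information pertaining to the inclusionary & exclusionary criteria will be included in the questionnaire". Recruitment under 8g also reaches people calling a Stanford clinic: "all families who call the Stanford clinic for services are asked about their willingness to be contacted for research". The clinic is not described further. Section 2e then says "this study will not hinder participants with a DSM-5 eating disorder from continuing or pursuing any outside treatment" while they are enrolled, and reports from earlier research that "there are stronger reductions in eating disorder symptoms for participants with a DSM-5 eating disorder than participants without an eating disorder".

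**Assessment and referral.** Section 2a lists the EDDI at baseline (step 3), posttest (step 5) and 3 months (step 6), each time described as measuring whether an eating disorder is present. Diagnostic interviews are named only at 3 months, and step 3 calls the baseline assessment survey-based. Section 2f says that, for participants "who meet criteria for a DSM-5 eating disorder at the termination of the study, the appropriate referrals will be provided". Section 10 lists referral information for local resources as a potential benefit, with no trigger and no time point. Section 2g says "study participation will be completed within 24-weeks, including a 3-month follow up after the conclusion of Body Project groups".

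**The concern.** There are two linked problems.

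First, the label and the entry rules describe different groups. If results are reported as applying to healthy women, they will describe a sample other than the one 8h admits. Section 2e itself says that women with and without a disorder respond differently, so the label affects how the results are read.

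Second, the study collects information on the presence of an eating disorder well before the point at which the protocol says what to do about it. A woman who is positive at baseline or posttest has no stated diagnosis-tied step at that time. Permission to seek outside care does not fill the gap, because Protocol 3a says that 80% of people with eating disorders never seek treatment. What is at stake is participant care and an accurate description of the sample, not the validity of the randomised comparison.

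**Working it through.** The plan gives no figure to reproduce. The check is a comparison of sections, followed by simple timing arithmetic.

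**Can a woman with a current eating disorder be enrolled?**
1. 8h: none of the four inclusion items concerns health, and there are no exclusions. She is eligible.
2. 8i: the questionnaire is confined to the 8h items, so it would not identify her.
3. 2a: the judgement that she suits the study comes before the baseline EDDI and has no stated health criterion.
4. 2e: the protocol expects such women to be enrolled.

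So 8a(iii) and 8f do not describe the group that 8h and 2e allow.

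**What follows a positive EDDI in the protocol text?**

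| Time of positive EDDI | Diagnosis-tied referral stated |
|---|---|
| Baseline (2a, step 3) | None at that time |
| Posttest (2a, step 5) | None at that time |
| 3 months (2a, step 6) | 2f, if criteria are met at study termination |

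Section 9 adds no action on a positive result. Its items on events for review and on triggers are N/A. It lets the investigator end participation judged harmful, which is not a referral.

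**How long, for a woman who completes?** Inputs are 4 weeks of sessions and a 3-month follow-up (8m), with 3 months taken as 13 weeks.
- Baseline to her last assessment: 4 + 13 = 17 weeks. This assumes that sessions start soon after baseline and that the 3 months run from the end of the groups, as 2g says.
- Upper limit on participation in 2g: 24 weeks.
- Posttest to her last assessment: about 13 weeks.

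**Who has no diagnosis-tied referral at all under 2f?** A woman positive at baseline or posttest who either does not reach the final assessment or no longer meets criteria there. The documents give no count of EDDI-positive women and no 3-month dropout figure, so this group cannot be sized.

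**The case against.** The strongest reply is that 2f answers a template question about care after the study, so mention of the study's end follows from the question. This stands in part: 2f does not tell staff to withhold earlier referral. A reader might infer that the protocol imposes a waiting period, but it does not. It is silent about earlier positive results, and the intervals above are what that silence implies if the text is followed as written.

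Second, the missing step may exist elsewhere. Section 8c sends information on risks, benefits and welfare to the consent forms, which are not in the review copy. Section 10 may mean that everyone, including dropouts, receives referral information. Section 8f foresees participants learning new things about their psychological health during the study. All this is possible, and it is why the point is limited to the available protocol text. None of these places ties a referral to an EDDI result or a date.

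Third, the baseline EDDI may be only a survey, so a positive result there may not be a confirmed diagnosis. That is fair, but offering referral information does not need a confirmed diagnosis.

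Fourth, one might infer that the low-risk statement depends on the healthy label. It does not: 9a(vii) makes essentially the same statement about participants without that word.

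Fifth, neither the aims nor the SAP uses the word healthy, so a misworded conclusion is a risk to avoid and not an error already made.

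**Conclusion.** The point holds as a minor one. The healthy label in 8a(iii) and 8f conflicts with 8h and 2e. The available protocol text also states no diagnosis-tied referral for an EDDI that is positive before the end. For a completer, the stated referral comes about 17 weeks after baseline, or up to 24 under 2g. For a woman who drops out or no longer meets criteria, none is stated. This rests on the protocol text alone and on reading the end of the study in 2f as her own last assessment.

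Three larger readings are tempting but not supported:
- **A count of women lost.** The SAP reports 12% to 24% missing at posttest, which on the planned 60 is 60 × 0.12 = 7.2 to 60 × 0.24 = 14.4. That covers all women at posttest. It is neither 3-month dropout nor a count of EDDI-positive women.
- **A wait of 22 to 26 weeks.** This takes the end of the study as the last participant's completion (9d): 8 months less 2 to 3 months of analysis (8m) leaves 5 to 6 months. It also needs enrolment on the first day. Section 9d separately ends each participant's data collection at her own completion, so the reading is strained.
- **Bias between arms.** Both arms have the same entry rules and 50/50 randomisation, and the SAP model adjusts for pretest. The mixed sample affects whom the result describes, not the virtual versus in-person contrast.

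**What to change.** 1. In 2f, state that referral information is offered after any positive EDDI, whether at baseline, posttest or 3 months, using the resources already mentioned in section 10. If the consent form already provides this, make 2f agree with it.
2. The SAP describes posttest data in the past tense, so those data exist. Check the EDDI results already collected and send the information to any positive woman not yet referred, including those who dropped out.
3. In 8a and 8f, replace the healthy label with wording that women with a current eating disorder may be enrolled, and word the study's conclusion for that mixed sample.

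The cost is a few sentences in 2f, 8a and 8f and one pass through data on file. The downside is a few more referrals, some to women whose survey-based EDDI would not be confirmed at interview.

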9. RISKS

a. Potential Risks

i. Investigational devices

N/A

ii. Investigational drugs

N/A

iii. Commercially available drugs, biologics, reagents or chemicals

N/A

iv. Procedures

N/A

v. Radioisotopes/radiation-producing machines

N/A

vi. Physical well-being

There are no risks to physical well-being

vii. Psychological well-being

Participants may feel distressed when disclosing personal information during the assessment visits or during the group sessions. Based on previous experience, the associated risk of this occurring is a very low and the effects would be short-lived. These assessments have been used by thousands of young women with almost no distressing outcomes. Participants have the option to not answer any question if they feel uncomfortable.

viii. Economic well-being

N/A

ix. Social well-being

There is a small chance that participants may be assigned to a group led by a peer educator that they know outside of the context of this program. When groups are assigned to the peer educators, we will ask them to check the list to ensure they do not have a personal relationship with any of the participants assigned to their group. In the case that they do, the participant will be placed into a different group led by a peer educator with whom they do not know.

Additionally, peer educators may know that a group member is participating in the program. However, they will be extensively trained on the importance of confidentiality and protecting participant information. The peer educator group leaders might know a group member from outside of the group and might discuss confidential information about that group member to others who are not part of the group. However, peer educators will be put through an application process and extensive training to ensure they understand the importance of protecting information and dealing with sensitive matters.

x. Overall evaluation of risk

Low risk

b. International Research Risk Procedures

N/A

c. Procedures to Minimize Risk

- i) If interested participants do not consent their information will not be retained.
- (ii) All electronic information will be maintained on password-protected files on encrypted devices at Stanford.
- (iii) Participants' data that will not contain PHI will be identified by assigned identification codes (ID numbers) that will not be determined by any personal identifiers so that participants' identification and privacy will be protected.
- (iv) Access to files and identifiers will be restricted to Stanford researchers involved in the study.
- (v) The study will protect against risks of confidentiality by securing all data containing PHI in locked files, assigning ID numbers for data collection, and reinforcing the policies of confidentiality among the study researchers according to Stanford's guidelines.

d. Study Conclusion

Data collection for each participant will terminate once they've completed the study (4 weeks of Body Project Sessions, posttest and 3 month follow up assessments). The entire study will terminate when all sessions assessments have been completed for all participants.

If the participant wants to terminate the experiment at any time, they can do so. If the investigator determines that participation would be harmful to the subject or investigator in any way, they can terminate the experiment.

e. Data Safety Monitoring Plan (DSMC)

i. Data and/or events subject to review

N/A

ii. Person(s) responsible for Data and Safety Monitoring

N/A

iii. Frequency of DSMB meetings

N/A

iv. Specific triggers or stopping rules

N/A

v. DSMB Reporting

N/A

vi. Will the Protocol Director be the only monitoring entity? (Y/N)

Yes

vii. Will a board, committee, or safety monitor be responsible for study monitoring? (Y/N)

No

f. Risks to Special Populations

N/A

10. BENEFITS

Because this is a prevention program, the most salient potential benefit is the reduction of eating disorder risk factors/symptoms and the potential prevention of future eating disorders in participants. Additionally, there is the potential benefit of altruism from participation in personally relevant research, a better understanding of eating disorders, and receiving referral information for local low/no cost resources for eating disorders and other mental health concerns.

11. PRIVACY AND CONFIDENTIALITY

All participant information and specimens are handled in compliance with the Health Insurance Portability and Accountability Act (HIPAA) and privacy policies of Stanford University, Stanford Health Care, and Stanford Children's Health.

The Body Project: Comparing the Effectiveness of an In-person and Virtually Delivered Intervention

NCT: 05794763

02/06/2023

Mixed effects modeling was used to control for potential lack of independence within cohort. Specifically, for each measure we fit the following model:

$$Posttest_{ij} = \beta_0 + b_j + \beta_1 cond_{ij} + \beta_2 Pretest_{ij} + e_{ij}$$

where  $Posttest_{ij}$  is the posttest score for participant  $i$  in cohort  $j$ ,  $cond_{ij}$  is an indicator variable taking on the value of 0 for control and 1 for treatment,  $Pretest_{ij}$  is the pretest score,  $b_j$  is the random intercept for cohort  $j$ , and  $e_{ij}$  is the residual. The intraclass correlation for cohort was approximately 0 for all measures, nonetheless, it was retained as this was a feature of the study design. Due to missingness at the posttest (ranged from 12% for number of eating symptoms to 24% for the other outcomes), multiple imputation was used (Graham, 2009). We imputed 50 datasets and applied Rubin's rules to pool results across the models. As a sensitivity analysis, models were fit using only participants with complete data. Models were fit in R (R Core Team, 2021) using the nlme package, the mice package was used for imputation (van Buuren, 2018) and plots were created using ggplot2 (Wickham, 2016).

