2. STUDY PROCEDURES

a. Procedures

1) Young adult females will learn about the study through the study team's recruitment efforts, including online advertisements through Facebook, Instagram, Craigslist, and

Reddit, flyers posted near college campuses flyers posted in high traffic areas on Stanford's campus (dorms, dining halls) and distributed/promoted by Vaden Student Health Services, listservs for different communities/clubs, social media platforms (Instagram, Facebook, Twitter), Reddit

2) Potential participants who express interest will be given a link to a secure online Qualtrics screening questionnaire for the research study (this link will also be available directly from advertising material). Upon completion of the questionnaire, potential participants will then be contacted via phone or email. After eligibility is determined, they will be scheduled for a consent and baseline assessment.

3) After it has been determined that potential participants are a good fit for the study and they have offered consent to participate, they will be instructed to complete a short survey-based assessment.

Assessments

- a) EDDI: A standardized measure that measures the presence of an eating disorder and the severity of the characteristic psychopathology of eating disorders.
- b) Survey: Demographics, Thin Ideal Internalization Scale, Body Dissatisfaction Scale, Positive and Negative Affect Scale and Dutch Restrained Eating Scale

4) All participants will receive the same 4 session eating disorder prevention program, albeit virtual groups or in-person groups. Participants will be randomized to a virtual delivery condition condition or an in-person delivery condition. Participants have a 50/50 chance of being randomized to either condition. Participants will be assigned to a 5–6-person group run by trained peer educators, and engage in 4 sessions of the Body Project over the course of 4 weeks. These sessions will take place either online using Zoom, a videoconferencing tool, or in-person on Stanford's campus (following university COVID-19 safety protocols and precautions).

5) Once the 4 sessions have been completed, participants will be contacted to complete a short set of post-test surveys.

Assessments

- a) EDDI: A standardized measure that measures the presence of an eating disorder and the severity of the characteristic psychopathology of eating disorders.

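### Does the SAP's single random intercept, for an undefined cohort, leave clustering by delivery group out of the virtual versus in-person comparison?

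*SAP*

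**What the plan says.** The SAP models each posttest score on condition and pretest, with a random intercept for cohort as its only random effect: "Mixed effects modeling was used to control for potential lack of independence within cohort". Condition carries both participant and cohort subscripts and "is an indicator variable taking on the value of 0 for control and 1 for treatment". On the size of the clustering it reports: "The intraclass correlation for cohort was approximately 0 for all measures, nonetheless, it was retained as this was a feature of the study design".

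The protocol does not mention cohorts. Its section 2a, item 4, describes the unit of delivery: "Participants will be assigned to a 5–6-person group run by trained peer educators". On format it says: "These sessions will take place either online using Zoom, a videoconferencing tool, or in-person". Each delivery group therefore sits inside one arm. Section 8a gives the planned size: "We expect to enroll 60 participants at Stanford". Randomisation is of individuals, 1:1.

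**The concern.** Members of a small discussion group share leaders, sessions and one another, so their outcomes may be correlated. Because each group belongs to one arm, that correlation enters the variance of the between-arm difference in full. A random intercept for the delivery group allows for it. A random intercept for a unit containing both arms does not, because a term shared by the two arms cannot absorb differences between groups nested within an arm.

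The SAP does not say which kind of unit cohort is. The subscripts on condition allow it to vary within a cohort, which would be impossible if cohort were a delivery group. If cohort were a both-arm unit, the standard error for virtual versus in-person would be too small. The reported ICC of about zero would also give little reassurance, since it would describe a different level.

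**Working it through.** **Nothing to reproduce.** The documents give no sample-size calculation, significance level, effect size or ICC identified as group-level. The group ICC (0, 0.05, 0.10) and the two-sided 5% level below are assumptions.

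**Inputs from the documents.** N = 60 (protocol 8a); groups of 5–6, mean 5.5 (protocol 2a); posttest missingness of 12% to 24% (SAP).

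- Number of groups: 60/6 = 10 to 60/5 = 12, so 5–6 per arm.
- Mean observed group size: m = 5.5 × 0.88 = 4.84 at 12% missing; 5.5 × 0.76 = 4.18 at 24% missing.

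**Reading A: cohort spans both arms, so group clustering is omitted.** Design effect DE = 1 + (m − 1) × ICC. The standard error is too small by 1 − 1/√DE. True type I error = 2 × [1 − Φ(1.96/√DE)].

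| Missing | Group ICC | DE | SE too small by | Type I error |
|---|---|---|---|---|
| 24% | 0 | 1 | 0% | 5.0% |
| 24% | 0.05 | 1 + 3.18 × 0.05 = 1.159 | 7.1% | 6.9% |
| 24% | 0.10 | 1 + 3.18 × 0.10 = 1.318 | 12.9% | 8.8% |
| 12% | 0 | 1 | 0% | 5.0% |
| 12% | 0.05 | 1 + 3.84 × 0.05 = 1.192 | 8.4% | 7.3% |
| 12% | 0.10 | 1 + 3.84 × 0.10 = 1.384 | 15.0% | 9.6% |

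Type I error reaches 6% when DE = (1.96/1.881)² = 1.086, that is at ICC = 0.086/3.18 = 0.027 (24% missing) or 0.086/3.84 = 0.022 (12% missing).

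**Reading B: cohort is the delivery group.** The SAP's model was simulated with 60 participants in 10 or 12 groups, 24% missing completely at random, pre-post correlation 0.6, 50 imputations on pretest and condition, Rubin pooling with complete-data degrees of freedom n − 3, and 4,000 trials per setting. Type I error was 3.6–4.2% at ICC 0, 4.6–5.2% at 0.05 and 5.8–6.7% at 0.10. At 4,000 trials the Monte Carlo margin near 5% is about 1.96 × √(0.05 × 0.95/4000) = 0.7 points. The test is therefore near nominal up to 0.05 and modestly liberal at 0.10.

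**Which reading the text supports.**

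- The SAP keeps the intercept because it belongs to the design. The delivery group is the only multi-person unit in the design as described. No wave, intake or calendar block appears in either document.
- The case for reading A is the double subscript on condition. The posttest, pretest and residual carry the same subscripts, and only the random intercept has a single one. This is common default notation for a two-level model.
- The labels around it are generic too: the equation codes the arms as control and treatment, whereas in the protocol both arms receive the same programme.
- The study calendar does not help. Eight months in all (protocol 8m), less 4 of participation and 2–3 of analysis, leaves 1–2 months for groups to start. Section 2g allows 24 weeks (about 5.5 months) of participation, which would leave −0.5 to +0.5 months. The SAP model also needs only the posttest, so its analysis need not wait for the 3-month follow-up.

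**The case for a change.** The strongest case for acting is that the unit decides whether the main standard error is valid, and that the near-zero ICC cannot settle the unit. In a simulation with one virtual and one in-person group per cohort, the estimated cohort ICC fell below 0.01 in 51% of trials when the true group ICC was 0.05, and in 41% when it was 0.10. A small cohort ICC is thus compatible with real group clustering if reading A holds. Generic notation also cuts both ways: if the equation came from a template, the word cohort might have come with it.

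The first part stands as logic: under reading A, the reported ICC would not clear the group level. Two things limit it. Those percentages are for a single outcome, whereas the SAP reports an ICC near zero for every measure. With five measures correlated 0.3–0.6 (an assumption) and two groups per cohort, all five estimates fall below 0.01 in 12–23% of trials at group ICC 0, against 2–7% at 0.10. The report therefore counts somewhat against an ICC as high as 0.10 in that layout. With two large waves it says little (24–34% against 15–23%). More important, the argument starts only once reading A is granted, and the documents give no both-arm unit to grant it to. The template point weakens confidence in any single word, but it does not supply such a unit.

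**Conclusion.** The concern does not hold as a fault in the plan. It is true that cohort is undefined, and the consequence of a both-arm cohort is correctly worked out: about 7% type I error at a group ICC of 0.05 and 9–10% at 0.10, instead of 5%. But those figures need both the less supported reading of the word and a group ICC that the documents do not give. On the better supported reading, cohort is the 5–6-person delivery group. The clustering is then already modelled, the reported ICC of about zero applies to it, and error rates are near nominal.

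What remains is a definition left unwritten. The SAP reports an estimated cohort ICC and observed missingness, so a cohort variable was already in the dataset when it was written. Whoever fits the model knows what that variable is, and a reader who doubts it can ask. A one-word ambiguity whose natural resolution leaves the analysis as it stands is no ground for changing the model. The conclusion rests on reading cohort as the delivery group; evidence that it was a unit shared by the two arms would reopen the point.
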